5.1.1.3.1 Endpoints for US

The efficacy endpoints for the United States analyses are described as follows. [REDACTED]

[REDACTED] y.

Table 5-14 US Analyses

Endpoint	Description	Timing	Methodology
P1	Pain freedom (PF) at 2 hours after the initial dose, defined as a reduction in headache severity from moderate/severe at baseline to no pain, at 2 hours after the initial dose	2 hours after the initial dose	Logistic regression model
P2	Absence of the most bothersome migraine-associated symptom (the most bothersome migraine-associated symptom will be identified at baseline for each participant) at 2 hours after the initial dose.	2 hours after the initial dose	Logistic regression model
S1	Pain relief (PR) at 2 hours after the initial dose, defined as the reduction of a moderate/severe migraine headache to a mild headache or to no headache, at 2 hours after the initial dose	2 hours after the initial dose	Logistic regression model
S2	Sustained pain relief (SPR) from 2 to 24 hours after the initial dose, defined as pain relief with no administration of either rescue medication or the second dose of IP, and with no occurrence thereafter of a moderate/severe headache during the relevant number of hours after dosing with the IP	2 to 24 hours after the initial dose	Logistic regression model
S3	Sustained pain freedom (SPF) from 2 to 24 hours after the initial dose, defined as pain freedom with no administration of either rescue medication or the second dose of IP, and with no occurrence thereafter of a mild/moderate/severe headache during the relevant number of hours after dosing with the IP	2 to 24 hours after the initial dose	Logistic regression model

Endpoint	Description	Timing	Methodology
S4a	Absence of photophobia at 2 hours after the initial dose	2 hours after the initial dose	Logistic regression model
S4b	Absence of phonophobia at 2 hours after the initial dose	2 hours after the initial dose	Logistic regression model
S4c	Absence of nausea at 2 hours after the initial dose	2 hours after the initial dose	Logistic regression model
■	[REDACTED]	[REDACTED]	[REDACTED]
■	[REDACTED]	[REDACTED]	[REDACTED]
■	[REDACTED]	[REDACTED]	[REDACTED]
■	[REDACTED]	[REDACTED]	[REDACTED]
■	[REDACTED]	[REDACTED]	[REDACTED]
■	[REDACTED]	[REDACTED]	[REDACTED]
■	[REDACTED]	[REDACTED]	[REDACTED]
■	[REDACTED]	[REDACTED]	[REDACTED]
■	[REDACTED]	[REDACTED]	[REDACTED]
■	[REDACTED]	[REDACTED]	[REDACTED]
■	[REDACTED]	[REDACTED]	[REDACTED]
■	[REDACTED]	[REDACTED]	[REDACTED]
■	[REDACTED]	[REDACTED]	[REDACTED]
■	[REDACTED]	[REDACTED]	[REDACTED]
■	[REDACTED]	[REDACTED]	[REDACTED]
■	[REDACTED]	[REDACTED]	[REDACTED]
■	[REDACTED]	[REDACTED]	[REDACTED]
■	[REDACTED]	[REDACTED]	[REDACTED]
■	[REDACTED]	[REDACTED]	[REDACTED]
■	[REDACTED]	[REDACTED]	[REDACTED]
■	[REDACTED]	[REDACTED]	[REDACTED]
■	[REDACTED]	[REDACTED]	[REDACTED]
■	[REDACTED]	[REDACTED]	[REDACTED]

Endpoint	Description	Timing	Methodology
[REDACTED]	[REDACTED]	[REDACTED]	[REDACTED]
[REDACTED]	[REDACTED]	[REDACTED]	[REDACTED]
[REDACTED]	[REDACTED]	[REDACTED]	[REDACTED]
[REDACTED]	[REDACTED]	[REDACTED]	[REDACTED]

Endpoint	Description	Timing	Methodology
[REDACTED]	[REDACTED]	[REDACTED]	[REDACTED]
[REDACTED]	[REDACTED]	[REDACTED]	[REDACTED]

Endpoint	Description	Timing	Methodology
[REDACTED]	[REDACTED]	[REDACTED]	[REDACTED]
[REDACTED]	[REDACTED]	[REDACTED]	[REDACTED]
[REDACTED]	[REDACTED]	[REDACTED]	[REDACTED]
[REDACTED]	[REDACTED]	[REDACTED]	[REDACTED]
[REDACTED]	[REDACTED]	[REDACTED]	[REDACTED]
[REDACTED]	[REDACTED]	[REDACTED]	[REDACTED]
[REDACTED]	[REDACTED]	[REDACTED]	[REDACTED]
[REDACTED]	[REDACTED]	[REDACTED]	[REDACTED]

Endpoint	Description	Timing	Methodology
[REDACTED]	[REDACTED]	[REDACTED]	[REDACTED]
[REDACTED]	[REDACTED]	[REDACTED]	[REDACTED]
[REDACTED]	[REDACTED]	[REDACTED]	[REDACTED]

Endpoint	Description	Timing	Methodology

█
	
dose.
 
[REDACTED]
	
[REDACTED]
	
[REDACTED]

█
	
[REDACTED]
	
[REDACTED]
	
[REDACTED]

A summary of the number and percentage of participants who took both the optional second dose and rescue medication within 24 (48) hours after the initial dose will also be provided by treatment sequence (placebo/placebo, ubrogepant 50 mg/50 mg, ubrogepant 50 mg/placebo, ubrogepant 100 mg/100 mg, ubrogepant100 mg/placebo). The denominator is the number of participants who took the optional second dose.

[REDACTED]

[REDACTED]

[REDACTED]

5.1.1.3.4 Multiple Comparisons Procedure for Primary and Secondary Endpoints

The overall familywise error rate (FWER) will be controlled at $\alpha = 0.05$ for the set of primary and secondary endpoint comparisons between each dose level of ubrogepant vs. placebo both for the US analyses and for the EU analyses.

A graphical approach by Bretz et al (2009) will be used to control the overall type I error rate for multiple comparisons across the ubrogepant doses and the primary and secondary efficacy endpoints. For the US analyses, the coprimary efficacy endpoints will serve as the gatekeepers of the secondary endpoints. [REDACTED]

[REDACTED] The secondary endpoints will be tested in the same order as they appear in the list of secondary endpoints, except for the 3 migraine-associated symptoms which will be treated at the same level to allow the recycling of weights among the 3 symptom endpoints. Recycling of weights between the 2 doses is also allowed.

Using graphical approach with the weighted Bonferroni-based closed test procedure, the endpoints are represented by circles with associated weights inside the circle. The weight is the fraction of α , representing local significance levels. The fraction in the rectangle, associated with a line connecting two circles, indicates the fraction of the local significance level of the circle at the beginning of the line which is added to the local significance level of the circle at the end of the line, if the null hypothesis at the beginning circle is rejected.

Figure 5-9 Multiple Comparisons Procedure for the US

[figure not shown]
[figure not shown]

Table 5-16 Multiple Comparisons Procedure Definitions for the US

Circle	Alternative Hypothesis	Objective	Weight	Local Significance Level
50mgP1	Primary Efficacy Endpoint 1 for 50 mg ubrogepant is significantly different from placebo	PO1	1/2	$\alpha*(1/2) = \alpha/2$
50mgP2	Primary Efficacy Endpoint 2 for 50 mg ubrogepant is significantly different from placebo	PO1	0	$\alpha*0 = 0$

50mgS1	Secondary Efficacy Endpoint 1 for 50 mg ubrogepant is significantly different from placebo	PO1	0	$\alpha^*0 = 0$
50mgS2	Secondary Efficacy Endpoint 2 for 50 mg ubrogepant is significantly different from placebo	PO1	0	$\alpha^*0 = 0$
50mgS3	Secondary Efficacy Endpoint 3 for 50 mg ubrogepant is significantly different from placebo	PO1	0	$\alpha^*0 = 0$
50mgS4a	Secondary Efficacy Endpoint 4a for 50 mg ubrogepant is significantly different from placebo	PO1	0	$\alpha^*0 = 0$
50mgS4b	Secondary Efficacy Endpoint 4b for 50 mg ubrogepant is significantly different from placebo	PO1	0	$\alpha^*0 = 0$
50mgS4c	Secondary Efficacy Endpoint 4c for 50 mg ubrogepant is significantly different from placebo	PO1	0	$\alpha^*0 = 0$
100mgP1	Primary Efficacy Endpoint 1 for 100 mg ubrogepant is significantly different from placebo	PO1	1/2	$\alpha^*(1/2) = \alpha/2$
100mgP2	Primary Efficacy Endpoint 2 for 100 mg ubrogepant is significantly different from placebo	PO1	0	$\alpha^*0 = 0$
100mgS1	Secondary Efficacy Endpoint 1 for 100 mg ubrogepant is significantly different from placebo	PO1	0	$\alpha^*0 = 0$
100mgS2	Secondary Efficacy Endpoint 2 for 100 mg ubrogepant is significantly different from placebo	PO1	0	$\alpha^*0 = 0$
100mgS3	Secondary Efficacy Endpoint 3 for 100 mg ubrogepant is significantly different from placebo	PO1	0	$\alpha^*0 = 0$
100mgS4a	Secondary Efficacy Endpoint 4a for 100 mg ubrogepant is significantly different from placebo	PO1	0	$\alpha^*0 = 0$
100mgS4b	Secondary Efficacy Endpoint 4b for 100 mg ubrogepant is significantly different from placebo	PO1	0	$\alpha^*0 = 0$
100mgS4c	Secondary Efficacy Endpoint 4c for 100 mg ubrogepant is significantly different from placebo	PO1	0	$\alpha^*0 = 0$

5.1.1.4.1 Study Treatment Exposure and Compliance

Study treatment exposure and compliance will be listed for the Safety Population.

A summary of treatment compliance to the first dose of study medication in terms of the number and percentage of participants who took 2 tablets instead of only 1 tablet will be provided by treatment group.

The listing of treatment exposure will indicate whether the participant took the optional second dose and PK dose in addition to the first dose.

[Redacted]	[Redacted]
[Redacted]	[Redacted]

[REDACTED]	[REDACTED]	[REDACTED]	[REDACTED]
[REDACTED]	[REDACTED]	[REDACTED]	[REDACTED]
[REDACTED]	[REDACTED]	[REDACTED]	[REDACTED]
[REDACTED]	[REDACTED]	[REDACTED]	[REDACTED]

[REDACTED]

[REDACTED]

[REDACTED]

[REDACTED]	[REDACTED]	[REDACTED]	[REDACTED]
[REDACTED]	[REDACTED]	[REDACTED]	[REDACTED]

[REDACTED]	[REDACTED]	[REDACTED]	[REDACTED]
[REDACTED]	[REDACTED]	[REDACTED]	[REDACTED]

[REDACTED]

[REDACTED]

[REDACTED]

[REDACTED]

[REDACTED]	[REDACTED]	[REDACTED]	[REDACTED]
[REDACTED]	[REDACTED]	[REDACTED]	[REDACTED]
[REDACTED]	[REDACTED]	[REDACTED]	[REDACTED]

[REDACTED]

[REDACTED]

[REDACTED]

[REDACTED]

[REDACTED]

[REDACTED]	[REDACTED]	[REDACTED]	[REDACTED]
[REDACTED]	[REDACTED]	[REDACTED]	[REDACTED]
[REDACTED]	[REDACTED]	[REDACTED]	[REDACTED]
[REDACTED]	[REDACTED]	[REDACTED]	[REDACTED]
[REDACTED]	[REDACTED]	[REDACTED]	[REDACTED]

[REDACTED]	[REDACTED]	[REDACTED]	[REDACTED]
------------	------------	------------	------------

[REDACTED]

[REDACTED]

[REDACTED]

[REDACTED]

[REDACTED]

[REDACTED]

[REDACTED]	[REDACTED]	[REDACTED]	[REDACTED]
------------	------------	------------	------------

[REDACTED]

[REDACTED]

[REDACTED]

[REDACTED]

[REDACTED]	[REDACTED]	[REDACTED]	[REDACTED]
------------	------------	------------	------------

[REDACTED]

5.1.1.5 Subgroup Analyses

A pooled analysis among triptan insufficient responders across ubrogepant pivotal studies will be conducted to demonstrate statistically significant efficacy in the triptan insufficient responders' population.

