7.3.1 Efficacy Analyses

7.3.1.1 Primary Efficacy Analyses

For each primary variable, the observed response proportions will be provided by treatment group. The primary efficacy variable of pain freedom at 2 hours after the initial dose will be analyzed using a logistic regression model with categorical terms for treatment group, historical triptan response (triptan responder, triptan insufficient responder, or triptan naïve), use of medication for migraine prevention (yes/no), and baseline headache severity (moderate or severe). The primary efficacy variable of absence of the most bothersome symptom at 2 hours after the initial dose will be analyzed using a similar logistic regression model with an additional categorical term for the underlying symptom that was identified as the most bothersome. If the logistic regression model fails to converge due to complete or quasi-complete separation, Firth’s penalized likelihood method (Firth, 1993) will be used. The logistic regression model will be referred to as the primary model.

The respective comparisons of the ubrogepant doses versus placebo, which are the formal tests of the efficacy hypotheses, will be conducted using the appropriate pairwise contrasts within the logistic regression model. Treatment comparisons will be based on the model-derived odds ratios and their associated 95% confidence intervals. Two-sided p-values will also be provided.

[REDACTED], the study will be considered a success if at least 1 ubrogepant dose is demonstrated to be superior to placebo on both coprimary variables after multiplicity adjustment.

[REDACTED]
[REDACTED]
[REDACTED].

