This statistical analysis plan (SAP) details comprehensive, technical specifications of the statistical analyses of the efficacy and safety data outlined and/or specified in the protocol amendment #3 dated 17May2017 of Study UBR-MD-01. Specifications of tables, figures, and data listings are contained in a separate document. [REDACTED]

This document is organized into 3 main sections:

1. Study overview
2. [Statistical Methodology and Study Endpoints](#)
3. [Data Handling and Analysis Conventions](#)

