5.1.1.1.3 Statistical Methodology

The methodologies defined below apply as specified to individual endpoints defined in this SAP. All statistical tests will be 2-sided hypothesis tests performed at the 5% level of significance for main effects. All confidence intervals will be 2-sided 95% confidence intervals, unless stated otherwise.

Table 5-2 Statistical Methodology

Methodology	Description
M1 Categorical counts	
 • Number of participants in individual categories 
 ○ Participants with ≥ 1 qualifying event counted once per individual category
M2 Categorical descriptives	
 • Number and percentage of participants in individual categories 
 ○ Participants with ≥ 1 qualifying event counted once per individual category • N1 if proportion denominator \neq number of participants in the population (standard percentage denominator) 
 ○ N1 = participants with non-missing baseline value
[REDACTED]	[REDACTED]
[REDACTED]	[REDACTED]
M5 Continuous descriptives	
 • N1, mean, standard deviation (SD), median, minimum, maximum • N1 = participants with non-missing value
M6 CFB descriptives	
 • Continuous descriptives for baseline, postbaseline, and change from baseline (CFB) values • N1 = participants with non-missing values at both baseline and the specified postbaseline analysis visit
[REDACTED]	[REDACTED]
M8 Responder	
 • Categorical descriptives using proportions for responders and nonresponders 
 ○ Nonresponders include: 
 ▪ Participants who do not meet responder criteria • N1 = all participants unless otherwise specified
[REDACTED]	[REDACTED]

Methodology	Description
	

CFB = change from baseline; ANCOVA = analysis of covariance.

Raw and derived data listings will be provided, and will be fully defined in the table, figure, and data listing specification document.

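### Does the pooled analysis of triptan insufficient responders need its own alpha and testing rule in this study's SAP?

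*SAP*

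**What the plan says.** SAP Section 5.1.1.5 (Subgroup Analyses) announces "A pooled analysis among triptan insufficient responders across ubrogepant pivotal studies" and says that it "will be conducted to demonstrate statistically significant efficacy in the triptan insufficient responders" population. That is the whole section, and no blackout falls inside it.

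Three other places bear on the point:

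- SAP Section 5.1.1.3.4 controls the familywise error rate at 0.05 "for the set of primary and secondary endpoint comparisons between each dose level of ubrogepant vs. placebo". Table 5-16 lists the US hypotheses and their starting weights.
- SAP Section 5.1.1.1.3 sets a general convention: "All statistical tests will be 2-sided hypothesis tests performed at the 5% level of significance for main effects". The same paragraph first limits its methods to individual endpoints that this SAP defines.
- Protocol Section 7.3.1.1 gives the model for the coprimary endpoints as "a logistic regression model with categorical terms for treatment group, historical triptan response", preventive medication use and baseline severity.

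SAP Table 5-8 lists previous triptan response, with insufficient responder as one of three levels, among the randomization strata.

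**The concern.** To set out to demonstrate statistical significance is to announce a test whose result will be claimed. Elsewhere the SAP is exact: it gives a starting weight for every US hypothesis and decision diagrams for the sustained endpoints. The one visible subgroup claim has no such rule.

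The other sections do not supply one. The controlled set does not include the pooled test. The general 5% convention provides no order and does not say which endpoint or dose counts. The coprimary model cannot be used unchanged, because triptan response is constant inside the subgroup and there is no term for study.

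If the endpoint, dose and level were chosen after the data were seen, a claim of efficacy in triptan insufficient responders could rest on the most favourable of several analyses. This trial's data would have contributed to it.

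**Working it through.** **1. Is this trial's own alpha affected?** The inputs are the starting weights in SAP Table 5-16 and the familywise level of 0.05 in Section 5.1.1.3.4.

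- Hypotheses: 8 endpoints (P1, P2, S1, S2, S3, S4a, S4b, S4c) × 2 doses = 16.
- Local level for P1 at 50 mg: 0.05 × 1/2 = 0.025. The same holds at 100 mg.
- The other 14 hypotheses start at 0.05 × 0 = 0.
- Sum: 0.025 + 0.025 + 14 × 0 = 0.05.

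This reproduces the stated familywise level exactly. All of the alpha is assigned to this study's own comparisons. None is reserved for the pooled test, and none is spent twice inside the graph.

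**2. Could the pooled test have been a node in this graph?** No. Section 5.1.1.5 describes data from several pivotal studies, while each hypothesis in Table 5-16 compares one dose with placebo in this study. The pooled result also depends on data from outside this trial. Standing outside the controlled set follows from what the analysis is.

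**3. Does the general 5% convention govern the pooled test?** This is not shown. Section 5.1.1.1.3 applies its methods to endpoints defined in this SAP, and no visible text defines a pooled endpoint. It would be wrong to conclude that the plan means to run the pooled test at an uncontrolled 5%.

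**4. Does the SAP promise to be complete on this point?** Section 4 says that it "details comprehensive, technical specifications of the statistical analyses of the efficacy and safety data outlined and/or specified in the protocol", and the sentence goes on to name Amendment 3 of this study. Completeness is claimed for this study's data, not for an integrated dataset.

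**5. Where would a pointer stand, and can it be seen?** Several likely places are blacked out:

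- the text in SAP Section 4 directly after the mention of a separate document for tables, figures and listings;
- parts of SAP Sections 5.1.1.1.3 and 5.1.1.3.4;
- the protocol's subgroup section, which the Amendment 1 summary lists as Section 7.4.

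Text that is blacked out cannot be counted as missing from the plan. The nine entries in SAP Section 7 do not settle the matter either. They are published papers and a guideline, and the list omits even this study's protocol.

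**6. Is the subgroup chosen from the data?** No. It is a randomization stratum (Table 5-8), and SAP Section 5.1 has the SAP approved before database lock. The population and the intention to pool were therefore on record before this trial's results were available.

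**The case for a change.** The strongest reply is that the missing rule could matter a great deal. Suppose that two doses share a placebo group at 1:1:1 (correlation 0.5), that each test is two-sided at 5% and only wins for the drug count, that endpoint correlations lie between 0.3 and 0.8, and that there is no true effect. The chance of a false claim is then:

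| Success rule | Chance of a false claim |
|---|---|
| One dose, one endpoint | 2.5% |
| Either dose, one endpoint | 4.5% |
| Same dose wins both coprimaries, either dose counts | 0.45–2.1% (4.5% if one coprimary truly works strongly at both doses) |
| Either dose, any of the 8 endpoints | 14–25% |

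The arithmetic is sound, but it does not describe this plan. Every rule in the table is supplied from outside, the 5% level is not shown to apply, and the designs of the other pivotal studies are not in these documents. The highest figures need a rule that nothing in the plan suggests. This trial's own success rule (Protocol Section 7.3.1.1) requires superiority on both coprimaries for at least one dose, after multiplicity adjustment. The table shows that a pooled plan must state its rule. It does not show that this SAP should.

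The point about the model carries little weight. A covariate that is constant in the subgroup drops out, and any analyst who pools trials would consider a term for study. A single-study model would not contain one.

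What stands is that the sentence is worded strongly and, as far as can be read, does not say where its rule is written. A citation of the governing pooled plan, or a description of the analysis as supportive with nominal p-values, would be a reasonable editorial courtesy.

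**Conclusion.** No change to the plan is needed. The gap is a cross-reference that cannot be seen, in a single-study document, to an analysis that a single-study document cannot govern. The familywise rate for this trial's 16 US comparisons stays at 0.05, and its primary and secondary conclusions are the same with or without the sentence.

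This rests on two points. The first is the reading that the rules for the pooled analysis belong in a plan for the pooled data. The second is that such a plan may exist or be cited under a blackout, which these documents neither confirm nor exclude. The finding is therefore not that error control for the pooled test is adequate, only that this SAP is not where to judge it. If the pooled result is later presented as confirmatory, it should be judged against the endpoint, dose contrasts, level and model fixed in its own plan, and against the date on which they were fixed.

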5.1.1.6 Interim Analyses

Not applicable.

[Redacted text block]

[Redacted text block]

[Redacted]	[Redacted]	[Redacted]	[Redacted]
[Redacted]	[Redacted]	[Redacted]	[Redacted]

[REDACTED]	[REDACTED]	[REDACTED]	[REDACTED]	[REDACTED]	[REDACTED]
------------	------------	------------	------------	------------	------------

5.2 Changes in the Conduct of the Study or Planned Analyses

Prior to database lock, there were no changes in study conduct or planned analyses from what was described in the protocol and detailed in the SAP.

5.2.1 Changes in the Conduct of the Study

Not applicable.

5.2.2 Changes to Analyses Prior to Database Lock

Not applicable.

6. Data Handling and Analysis Conventions

6.1 Study Treatment Conventions

6.1.1 Analysis Days

Treatment day is defined as follows:

Table 6-1 Analysis Day Definitions

Term	Description
Treatment Day	Relative to treatment start date If analysis date \geq treatment start date: 
 • Day = analysis date – treatment start date + 1 
 ○ Day 1 = treatment start date If analysis date < treatment start date: 
 • Day = analysis date – treatment start date 
 ○ Day -1 = day before treatment start date ○ There is no Day 0

6.1.2 Missing/Incomplete Treatment End Date

If the investigator is unable to provide the treatment end date, treatment end date will be imputed to the last available dosing record date.

6.2 Analysis Visit Windows

6.2.1 Efficacy

The analysis visit windows for efficacy endpoints are defined as follows:

Table 6-2 Efficacy Analysis Visit Definitions

Analysis Phase	Analysis Visit (Derived)	Study Hour (eDiary)	Window
Pretreatment	Baseline	Pre-dose	Based on nominal timepoints recorded in eDiary
Treatment	0.5 hour post-dose	0.5 hour post-dose	
	1 hour post-dose	1 hour post-dose	
	1.5 hours post-dose	1.5 hours post-dose	
	2 hours post-dose	2 hours post-dose	
	3 hours post-dose	3 hours post-dose	
	4 hours post-dose	4 hours post-dose	
	6 hours post-dose	6 hours post-dose	
	8 hours post-dose	8 hours post-dose	
	24 hours post-dose	24 hours post-dose	
48 hours post-dose	48 hours post-dose		

[Redacted]

[Redacted]	[Redacted]	[Redacted]	[Redacted]	[Redacted]
[Redacted]	[Redacted]	[Redacted]	[Redacted]	[Redacted]
[Redacted]	[Redacted]	[Redacted]	[Redacted]	[Redacted]
[Redacted]	[Redacted]	[Redacted]	[Redacted]	[Redacted]

[Redacted]

- [Redacted]
- [Redacted]
- [Redacted]

[Redacted]

[Redacted]	[Redacted]	[Redacted]	[Redacted]	[Redacted]	[Redacted]
[Redacted]	[Redacted]	[Redacted]	[Redacted]	[Redacted]	[Redacted]
[Redacted]	[Redacted]	[Redacted]	[Redacted]	[Redacted]	[Redacted]
[Redacted]	[Redacted]	[Redacted]	[Redacted]	[Redacted]	[Redacted]
[Redacted]	[Redacted]	[Redacted]	[Redacted]	[Redacted]	[Redacted]
[Redacted]	[Redacted]	[Redacted]	[Redacted]	[Redacted]	[Redacted]
[Redacted]	[Redacted]	[Redacted]	[Redacted]	[Redacted]	[Redacted]
[Redacted]	[Redacted]	[Redacted]	[Redacted]	[Redacted]	[Redacted]

[Redacted]

[REDACTED]

[REDACTED]

[REDACTED]

[REDACTED]

[REDACTED]

[REDACTED]	[REDACTED]	[REDACTED]	[REDACTED]	[REDACTED]
[REDACTED]	[REDACTED]	[REDACTED]	[REDACTED]	[REDACTED]
	[REDACTED]	[REDACTED]	[REDACTED]	[REDACTED]
	[REDACTED]	[REDACTED]	[REDACTED]	[REDACTED]
	[REDACTED]	[REDACTED]	[REDACTED]	[REDACTED]
	[REDACTED]	[REDACTED]	[REDACTED]	[REDACTED]
	[REDACTED]	[REDACTED]	[REDACTED]	[REDACTED]
	[REDACTED]	[REDACTED]	[REDACTED]	[REDACTED]
	[REDACTED]	[REDACTED]	[REDACTED]	[REDACTED]
	[REDACTED]	[REDACTED]	[REDACTED]	[REDACTED]
	[REDACTED]	[REDACTED]	[REDACTED]	[REDACTED]
[REDACTED]	[REDACTED]	[REDACTED]	[REDACTED]	[REDACTED]
	[REDACTED]	[REDACTED]	[REDACTED]	[REDACTED]
	[REDACTED]	[REDACTED]	[REDACTED]	[REDACTED]
	[REDACTED]	[REDACTED]	[REDACTED]	[REDACTED]
	[REDACTED]	[REDACTED]	[REDACTED]	[REDACTED]
	[REDACTED]	[REDACTED]	[REDACTED]	[REDACTED]
	[REDACTED]	[REDACTED]	[REDACTED]	[REDACTED]
	[REDACTED]	[REDACTED]	[REDACTED]	[REDACTED]
	[REDACTED]	[REDACTED]	[REDACTED]	[REDACTED]

[REDACTED]	[REDACTED]	[REDACTED]	[REDACTED]	[REDACTED]
[REDACTED]	[REDACTED]	[REDACTED]	[REDACTED]	[REDACTED]
	[REDACTED]	[REDACTED]	[REDACTED]	[REDACTED]
	[REDACTED]	[REDACTED]	[REDACTED]	[REDACTED]
	[REDACTED]	[REDACTED]	[REDACTED]	[REDACTED]
	[REDACTED]	[REDACTED]	[REDACTED]	[REDACTED]
	[REDACTED]	[REDACTED]	[REDACTED]	[REDACTED]
	[REDACTED]	[REDACTED]	[REDACTED]	[REDACTED]
	[REDACTED]	[REDACTED]	[REDACTED]	[REDACTED]
	[REDACTED]	[REDACTED]	[REDACTED]	[REDACTED]
	[REDACTED]	[REDACTED]	[REDACTED]	[REDACTED]
	[REDACTED]	[REDACTED]	[REDACTED]	[REDACTED]
	[REDACTED]	[REDACTED]	[REDACTED]	[REDACTED]
[REDACTED]	[REDACTED]	[REDACTED]	[REDACTED]	[REDACTED]
	[REDACTED]	[REDACTED]	[REDACTED]	[REDACTED]
	[REDACTED]	[REDACTED]	[REDACTED]	[REDACTED]
	[REDACTED]	[REDACTED]	[REDACTED]	[REDACTED]

[REDACTED]
[REDACTED]
[REDACTED]

[REDACTED] [REDACTED]
[REDACTED]
[REDACTED]

[REDACTED] [REDACTED]

[REDACTED]	[REDACTED]
[REDACTED]	[REDACTED]
	[REDACTED]
	[REDACTED]
	[REDACTED]
	[REDACTED]
	[REDACTED]

[REDACTED]	[REDACTED]
[REDACTED]	[REDACTED]

[REDACTED]

[REDACTED]

[REDACTED]

[REDACTED]	[REDACTED]
[REDACTED]	[REDACTED]
[REDACTED]	[REDACTED]
[REDACTED]	[REDACTED]

[REDACTED]

[REDACTED]

[REDACTED]

[REDACTED]

[REDACTED]	[REDACTED]	[REDACTED]	[REDACTED]
[REDACTED]	[REDACTED]	[REDACTED]	[REDACTED]
[REDACTED]	[REDACTED]	[REDACTED]	[REDACTED]

[REDACTED]

[REDACTED]

[REDACTED]

[REDACTED]

[REDACTED]

[REDACTED]	[REDACTED]	[REDACTED]	[REDACTED]
[REDACTED]	[REDACTED]	[REDACTED]	[REDACTED]
[REDACTED]	[REDACTED]	[REDACTED]	[REDACTED]
[REDACTED]	[REDACTED]	[REDACTED]	[REDACTED]

[REDACTED]

[REDACTED]

[REDACTED]

[REDACTED]

[REDACTED]

[REDACTED]	[REDACTED]	[REDACTED]	[REDACTED]
[REDACTED]	[REDACTED]	[REDACTED]	[REDACTED]
[REDACTED]	[REDACTED]	[REDACTED]	[REDACTED]

[REDACTED]

